**Figure 2. Hypothetical Data Illustrating the Primary Hypothesis**

#### 11.1.2 Secondary Hypothesis

- We hypothesize that among this study population of participants with TMD, the efficacy of propranolol will vary according to the number of LPS haplotypes of the COMT gene.
- We hypothesize that, compared with participants in the placebo-treated arm, participants in the propranolol-treated arm will have more favorable secondary endpoints, namely: (1) reduction in additional ratings of pain; (2) reduction in examiner-assessed levels of

pain sensitivity (pressure and heat pain sensitivity); (3) better participant ratings of physical function, emotional function, and global improvement; and (4) less frequent use of rescue medications and over-the-counter medications for pain.

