The participants' use of rescue medications for TMD pain as well as over-the-counter analysis as well as over-the-counter analysis as well as over-the-counter analysis. (namely, NSAIDs, acetaminophen, and aspirin) for the treatment of any type of pain during a period from V1 to V4 will be summarized by treatment group, both overall and by study visit. The number of days on over-the counter analgesics and the number of days on over-the counter analgesics as a ratio of days on study drug will be summarized (n, mean and standard error) by treatment group, both overall and by study visit. Log-transformed linear regression models will test for treatment group effects on the total number of days a participant is on rescue medications for the treatment of TMD-related pain and (in a separate analysis) for over-the-counter analgesics for the treatment of any pain. The days on rescue medications (or over-the-counter analgesics for any pain) will be log-transformed and used as the dependent variable. If there are some participants with 0 days on rescue medications (or over-the-counter analgesics), then a log(x+1) transformation of days will be used to prevent log(0) values. Study site, mean pain index at V1, and days on study (log-scale) will be used as covariates in the statistical models. Adjusted mean estimates and their 95% confidence intervals of the model adjusted days on rescue medications (or analgesics for any pain) will be reported with their treatment group effect p-values. If residual analysis suggests that model assumptions are unreasonable, then the following alternative model will be used to test for treatment group effects on the use of rescue medications (or over-the-counter analgesics for any pain). This alternative model will be a generalized linear mixed model using a negative binomial link with days on rescue medications (or over-the-counter analgesics for any pain) as the dependent variable and covariates for study site, mean pain index at V1, and for days on study.

Version 3.0 Page 16 of 25

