There are approximately 20 participants that were enrolled early at UB who did not have the "type of pain" documented when taking over-the-counter analgesics. It cannot be known whether the over-the-counter analgesics were taken due to TMD pain (i.e., rescue medications) and thus these 20 participants will be excluded from the above treatment group effects on the rescue medication use analysis. These subjects will be included in the use of over-the-counter analgesics for any pain.

All of the above secondary efficacy analyses are secondary to and supportive of the primary hypothesis analysis, and thus no statistical corrections will be made for multiplicity for any of the secondary analyses. P-values ≤ 0.05 will be considered statistically significant.

Additional secondary analyses of the incidence of adverse events are described in Section 9.

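### SAP 8.3.2 drops about 20 early UB participants from the rescue-medication test by a rule that, read literally, depends on analgesic use after randomization.

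*SAP*

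**What the plan says.** Protocol 11.1.2 hypothesizes that the propranolol arm will show "less frequent use of rescue medications and over-the-counter medications for pain". Protocol 11.4.2 plans treatment comparisons of days on rescue medication for TMD-related pain and of days on over-the-counter analgesics for any pain. It mentions no exclusion.

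SAP 8.3.2 gives the detail. The outcome is "the total number of days a participant is on rescue medications for the treatment of TMD-related pain", counted from V1 to V4 and log-transformed. Participants with no days of use remain in the model: "If there are some participants with 0 days on rescue medications (or over-the-counter analgesics), then a log(x+1) transformation of days will be used". On adjustment: "Study site, mean pain index at V1, and days on study (log-scale) will be used as covariates in the statistical models". There is no term for enrolment period.

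The same section then describes a data gap: "There are approximately 20 participants that were enrolled early at UB who did not have the 'type of pain' documented when taking over-the-counter analgesics". Because the reason for use is unknown, "thus these 20 participants will be excluded from the above treatment group effects on the rescue medication use analysis". For the other comparison, "These subjects will be included in the use of over-the-counter analgesics for any pain".

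The SAP gives no enrolment cut-off, no split of the 20 by arm and no count of early UB enrollees who took nothing. It plans no sensitivity analysis for the gap. P-values at or below 0.05 count as significant, without multiplicity correction. SAP section 11 records no changes from the protocol's analyses.

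**The concern.** The group is identified by two features: early enrolment at UB, and a missing pain type on analgesic records. The first is fixed before randomization. The second requires that an analgesic was taken, and analgesic use feeds the outcome being tested. A person who took nothing has no record with a missing pain type. On the literal text that person is outside the exclusion and enters with zero days.

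Within the early UB cohort, users would then leave and non-users stay. If the arms differ in any over-the-counter use, they lose different numbers of users and keep different numbers of zeros. Less use on propranolol is the trial's own hypothesis. Use for other pain could also differ, since Protocol 5.1 lists migraine among the drug's approved indications. A difference in other-pain use alone could then show up as a difference in TMD rescue use.

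**Working it through.** **Plan's own figure.** None exists. The power statements in Protocol 11.2 and SAP 2.6 concern the pain index and the haplotype interaction, not rescue medication.

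**Inputs.** From the documents: 200 randomized, 1:1, stratified by site; about 20 excluded; log(days+1) outcome; alpha 0.05. Assumed, because the documents do not give them: number of early UB enrollees, use rates by arm and days of use.

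**Step 1: ratio of mean days, no TMD effect.** Let n be participants per arm outside the early cohort, m their mean rescue days, and z the early non-users kept in that arm. The expected arm mean after exclusion is n·m/(n+z). With equal m, the drug/placebo ratio is (n + z placebo)/(n + z drug).

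- Cohort 25, any use 70% drug, 85% placebo: n = 87.5, z = 3.75 and 1.875. Ratio 89.375/91.25 = 0.979; excluded 8.75 + 10.625 = 19.4.
- Cohort 30, same rates: 87.25/89.5 = 0.975; excluded 23.25.
- Cohort 25, 50% and 80%: 90/93.75 = 0.960; excluded 16.25.
- Cohort 30, 50% and 80%: 88/92.5 = 0.951; excluded 19.5.

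The true ratio is 1.00. Only the first and last cases give close to 20 exclusions.

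**Step 2: the SAP's scale.** The SAP models log(days+1), so a simulation was run: 4,000 trials per scenario, N = 200, 66 assumed at UB, linear model on treatment and site. V1 pain index and days on study were left out. Mean days among users were 10 in both arms without a TMD effect, and 8 on drug against 12 on placebo with a benefit. Cells show the mean estimate, with the rejection rate in parentheses.

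| Assumed scenario (drug v placebo) | Early UB | Excluded, drug/placebo | No exclusion | Users only excluded | Whole cohort excluded |
|---|---|---|---|---|---|
| Equal use: TMD 40%, other pain 20% | 40 | 10.4/10.4 | 0.001 (0.053) | 0.000 (0.055) | 0.000 (0.057) |
| Equal use: TMD 50%, other pain 40% | 28 | 9.8/9.8 | -0.005 (0.045) | -0.005 (0.046) | -0.005 (0.048) |
| TMD 40% both; other pain 15% v 45% | 40 | 9.8/13.4 | 0.000 (0.050) | -0.022 (0.050) | -0.002 (0.051) |
| TMD 50% both; other pain 20% v 60% | 28 | 8.5/11.2 | 0.003 (0.048) | -0.024 (0.050) | 0.002 (0.048) |
| TMD 35% v 55%; other pain 10% both | 40 | 8.3/11.9 | -0.552 (0.927) | -0.516 (0.871) | -0.554 (0.852) |
| TMD 35% v 55%; other pain 15% v 30% | 36 | 8.0/12.4 | -0.552 (0.923) | -0.535 (0.890) | -0.551 (0.863) |
| TMD 50% v 70%; other pain 20% both | 30 | 9.0/11.4 | -0.601 (0.951) | -0.598 (0.924) | -0.602 (0.907) |

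The Monte Carlo standard error of a 0.05 rejection rate is √(0.05 × 0.95/4000) = 0.003.

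**Step 3: reading the table.**

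- Equal use: no bias, and the test keeps its size.
- No TMD effect but less other-pain use on drug: shifts of -0.022 and -0.024 - 0.003 = -0.027 toward the drug.
- Real benefit: shrinkage of 0.036/0.552 = 7%, 0.017/0.552 = 3% and 0.003/0.601 = 0.5%.
- Whole-cohort exclusion agrees with no exclusion to within 0.002 in every row.

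Further runs with cohorts of 25 and 30 (6,000 per scenario; any use 70% v 85% or 50% v 80%) gave shifts of -0.02 to -0.03 with no TMD effect. Type I error was 0.048 to 0.057, against 0.047 to 0.052 without exclusion. With a true ratio of about 0.79, the shift was about -0.015 on -0.30, or 5% toward the drug.

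Two forces explain the mixed direction. Retained zeros dilute both arms' means, which shrinks a log difference. More retained zeros in the lower-use arm pull the estimate toward that arm. The assumed rates decide which dominates.

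**Step 4: sample loss.** Dropping 20 of 200 raises the variance by 200/180 - 1 = 11% on either reading of the rule.

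**The case against.** The best defence is that the SAP may describe a whole cohort: people enrolled at UB before pain type was recorded. Exclusion would then rest on enrolment time, which precedes randomization, and the comparison among the rest would be intact. The SAP also discloses the gap, gives its reason, and keeps these participants in the any-pain analysis. The test is labelled supportive of the primary analysis.

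The ambiguity stands. The wording leans toward users, because it speaks of analgesics having been taken, but it does not rule out the cohort reading. The any-pain analysis limits the consequence but answers a different question from TMD rescue use.

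A reader might infer three stronger things that the documents do not support.

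- That early UB non-users are kept as zeros. The SAP never says so, nor that such participants exist. This follows only from combining the literal exclusion with the log(x+1) rule.
- That the exclusion favours propranolol. No use rates or arm split are given, the migraine route is a conjecture without a figure, and the simulated shift goes either way under a real benefit.
- That false-positive risk rises. Type I error stayed near 0.05 in every scenario run.

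The loss of about 10% of the sample is not an argument for the change, since excluding the whole cohort loses more.

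**Conclusion.** The concern holds in a conditional form. Read literally, the rule conditions exclusion on post-randomization use related to the outcome, and nothing in the plan would show whether that matters. If the 20 are the entire early UB cohort, this bias disappears and a sentence in the SAP settles it. Otherwise bias requires any-use rates that differ by arm. Its size then rests wholly on assumed cohort sizes (25 to 40) and use rates: about 0.02 to 0.03 log units with no TMD effect, and 0 to 7% of a real effect, in a direction the documents cannot settle. This is a small defect in a secondary analysis. It deserves correction because the remedy is cheap and makes exclusion independent of use.

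**What to change.** In SAP 8.3.2:

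1. Define the affected cohort by UB enrolment date or form version. Exclude all of it, users and non-users alike, from the TMD rescue-medication test.
2. Report the number excluded by arm.
3. Add two sensitivity runs in the full ITT population (the SAP's default under 8.3, not all 200 randomized). Count undocumented analgesic days as all TMD pain in one run and as none in the other. If they differ, describe the rescue-use result as sensitive to the missing information.

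The two runs bound each participant's count under one assumption for both arms. They do not cover assumptions that differ by arm.

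Cost: SAP wording, two model runs, and the loss of any early UB non-users from the main run. In the simulated benefit scenarios, power fell from 0.871 to 0.852, 0.890 to 0.863 and 0.924 to 0.907 when the exclusion moved from users only to the whole cohort. If the 20 already are the whole cohort, no further participants are lost.

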8.3.3 Exploratory Efficacy Analyses

The mixed model described for the secondary hypothesis of the LPS and Val/Met haplotypes will be modified by specifying genetic variants for the *COMT* promoter, *ADRB2* gene, and *ADRB3* gene. Other genetic variants may also be included in the mixed model. The only difference in these mixed model analyses is that the *ADRB2* and *ADRB3* gene types will be included as categorical fixed effects rather than the linear continuous fixed effects in the LPS and Val/Met haplotype mixed models.

Other stratum-specific estimates of treatment effect will be explored in an analogous manner, namely through the use of mixed models in which the stratification variable is a categorical fixed effect. Each stratum will be a mutually exclusive category of study participants, classified according to the following characteristics assessed either at V0 or V1:

- Body Mass Index, computed from measurements recorded at V1, will be used to create two strata, with the dichotomy based on one of two established thresholds ≥25 or ≥30. The decision as to which threshold will be made after inspecting the distribution of BMI, and select the threshold that is closest to the median.
- Smoking status, assessed using the Smoking questionnaire completed at V0, will be used to create two strata: current tobacco smokers or not (the latter therefore including former smokers and never smokers). Smokeless tobacco and other sources of nicotine will not be used for this classification.
- Migraine headache will be classified using responses to the headache questionnaire (HAQ) administered at V1. Two strata will be created, classified according to presence or absence of one or more of four types of migraine sub-types (Migraine without aura, Migraine with aura, Chronic migraine, or Probable migraine without aura).
- Degree of examiner-assessed tenderness to body palpation, recorded at Item 4 of the Fibromyalgia Questionnaire at V0, will be used to create two strata, based as closely as possible on a median split of the total number of tender points.

Version 3.0 Page 17 of 25

- Published scoring algorithms will be used to compute the catastrophizing subscale of the revised Coping Strategies Questionnaire (CSQ-R) measured at V1. The two strata will be based as closely as possible on a median split of the subscale score.
- Self-rated general health at V1, reported at item 1 of the SF-12v2 questionnaire, will be used to create two strata based as closely as possible on a median split of the ordinal rating (high, low).
- Anxiety and depression as measured using the two subscales of the Hospital Anxiety and Depression Scale (HADS) administered at V1. Two strata will be created based as closely as possible on a median split of each of the subscale scores (high, low).
- Sleep quality, as measured using the Global Score of the Pittsburgh Sleep Quality Index (PSQI) administered at V1. Two strata will created based as closely as possible on a median split of Global Score (high, low).
- Subjects' rating of confidence in treatment outcome reported at V1 will be used to create two strata based as closely as possible on a median split of the ordinal rating (high, low).

Exploratory analyses of the incidence of adverse events are described in Section 9.

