#### **11.4.3 Analysis of the Exploratory Hypotheses**

The exploratory hypotheses will extend the analytical procedures described above. In summary:

- The linear mixed model described for the secondary hypothesis will be modified by specifying genetic variants including, but not limited to the COMT gene promoter and the ADRB2 and ADRB3 genes.
- Other phenotypes will be evaluated as potential treatment effect modifiers using a similar strategy in which linear mixed models will test for phenotype-by-treatment interactions. Each phenotype will be categorized based on characteristics assessed either at V0 or V1. The phenotypes are: body mass index; smoking; migraine headache; tenderness to body palpation; catastrophizing subscale of the CSQ-R questionnaire; self-rated general health from the SF-12v2 questionnaire; anxiety and depression subscales from the HADS questionnaire; sleep quality from the PSQI questionnaire; and subjects' rating of confidence in treatment outcome. Full details are provided in the Statistical Analysis Plan.

The exploratory analysis will further explore the results, insights, or new questions that may arise during the study's analyses and will not be limited to the exploratory analyses listed above.

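### Six numeric effect modifiers in SAP 8.3.3 are tested only as two strata; adding a prespecified continuous contrast at V4 would recover information at little cost

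*SAP*

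**What the plan says.** Protocol 11.4.3 states that "linear mixed models will test for phenotype-by-treatment interactions". The same bullet says that every phenotype will be put into categories using V0 or V1 data, and leaves full details to the SAP. The section closes by leaving the list of exploratory analyses open.

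SAP 8.3.3 carries this out: "Other stratum-specific estimates of treatment effect will be explored in an analogous manner". The grouping variable enters each model as a factor, and every listed phenotype gets two strata. Six of them are numeric:

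- **BMI:** cut at 25 or 30; after inspecting the distribution, the team will "select the threshold that is closest to the median".
- **Tender-point count:** "will be used to create two strata, based as closely as possible on a median split of the total number of tender points".
- **CSQ-R catastrophizing:** "The two strata will be based as closely as possible on a median split of the subscale score".
- **HADS anxiety, HADS depression and PSQI global score:** a median split each.

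The other four are two yes/no variables (smoking, migraine) and two ordinal ratings (general health, confidence in treatment outcome). No continuous version is given for any phenotype. By contrast, SAP 8.3.2 fits the LPS haplotype count as both a linear and a categorical term and names a contrast for the interaction at V4.

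**The concern.** The exploratory objective is to learn whether efficacy varies with these characteristics. Cutting a many-valued score in two treats everyone on one side of the cut as alike. If modification is roughly linear, this makes a real modifier harder to detect, in a trial whose only stated interaction power, for the haplotype, is already just 61%. The haplotype count has three levels and is tried as a linear term; six scores with more values are not.

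What is at stake is efficiency in exploratory tests, not bias. Protocol 11.4.3 would permit a continuous analysis later, but one that the SAP does not name would not be prespecified.

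**Working it through.** **Step 1: reproduce the plan's interaction power.** Inputs from the table and footnote in Protocol 11.2: haplotype cells of 30, 50 and 20 per arm; drug-minus-placebo net change of 1080, 540 and 0 in absolute value; SD 1190; alpha 0.05, taken as two-sided.

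- Weights n₁n₂/(n₁+n₂): 15, 25, 10.
- Weighted mean effect: (15×1080 + 25×540 + 10×0)/50 = 594.
- Noncentrality: [15×486² + 25×54² + 10×594²]/1190² = 7,144,200/1,416,100 = 5.045.
- Power by noncentral F: 60.8% with 1 df (linear in copies), 50.1% with 2 df (three categories).

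The stated 61% therefore matches a linear term.

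**Step 2: information kept by a split.** For a linear modifier X, the efficiency of the split relative to the continuous term is r² = corr(X, I[X > cut])². The documents give no distributions, so the shapes are assumed. Power after the split is Φ((1.96 + 0.279)√r² − 1.96), where 0.279 is the normal quantile for 61%.

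| Assumed shape, cut at median | r² | Loss | 200 count as | 61% becomes |
|---|---|---|---|---|
| Uniform | 3/4 = 0.750 | 25% | 150 | 49% |
| Normal | 2/π = 0.637 | 36% | 127 | 43% |
| Gamma, shape 2 | 0.553 | 45% | 111 | 38% |
| Exponential | (ln 2)² = 0.480 | 52% | 96 | 34% |
| Lognormal, log-SD 0.75 | 0.396 | 60% | 79 | 29% |

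Simulation at N = 200 (4,000 runs per shape) gave, continuous v split, 61% v 49% (uniform), 60% v 41% (normal) and 58% v 33% (exponential).

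**Step 3: BMI.** BMI is not split at its median, so the table does not apply to it directly. For a normal variable cut at proportion p, r² = φ(z)²/[p(1−p)]. The loss is 38% for a 40/60 cut, 42% for 30/70 and 51% for 20/80.

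**Step 4: shapes other than linear.** Simulated power, continuous v split, with n = 180 (200 less the 10% loss in Protocol 11.2) and the effect sized for 80% power if its true shape were fitted:

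| True effect | Uniform | Normal | Gamma(2) | Exponential |
|---|---|---|---|---|
| Linear | 79 v 66 | 79 v 59 | 77 v 52 | 76 v 46 |
| Saturating, tanh(x) | 78 v 71 | 75 v 67 | 71 v 68 | 68 v 66 |
| Step at the median | 66 v 74 | 59 v 73 | 53 v 73 | 47 v 73 |
| Step at the 69th percentile | 59 v 44 | 56 v 45 | 60 v 45 | 58 v 45 |

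Here x is the score in SD units. For skewed scores, the saturating comparison depends on where the curve is centred. At tanh(1.5x) centred on the median, the information kept (continuous v split) is 78% v 83% for gamma(2) and 71% v 82% for exponential. Centred on the mean, it is 83% v 78% and 78% v 73%.

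**The case against.** The best case for the plan has four parts.

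- **The SAP follows the protocol.** Because Protocol 11.4.3 both plans interaction tests and calls for categories, a reader who sees only the first might infer a breach. The documents do not support that: the planned test is an interaction with a categorized phenotype, and the strata serve the SAP's aim of estimates by stratum. This stands in full.
- **The effect shape is unknown.** Neither coding is best for every shape. The linear case shows the largest loss for skewed scores, yet those are the scores for which mild saturation centred at the median cuts the gain to 2 or 3 points of power. A step at the cut favours the split. This stands, and it argues for reporting both codings.
- **The V4 target is arguably there already.** The phenotype models are to be analogous to the genetic ones, for which SAP 8.3.2 names a contrast at V4. A reader might infer that no target visit is set; the fairer reading is that it is inherited. What is missing is the continuous coding.
- **The 61% is borrowed.** It rests on pilot haplotype effects. No document gives an effect size for BMI, tender points, CSQ-R, HADS or PSQI, so the reduced powers are illustrations and not estimates for this trial.

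**Conclusion.** The point holds as a cheap improvement to exploratory analyses. Under an assumed linear modifier, a median split discards 25% to 52% of the information across the uniform, normal, gamma(2) and exponential shapes. The 52% is the exponential case and should not be read as a ceiling: a lognormal score with log-SD 0.75 loses 60%. These figures apply to the five median-split measures; BMI's loss depends on where 25 or 30 falls in its distribution.

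Two stronger inferences are not supported. The documents do not show that the continuous term is the better test, since they give neither distributions nor effect shapes. Nor do they justify reducing the strata to display only, because that would replace the categorized test that Protocol 11.4.3 describes. No primary or secondary conclusion is affected.

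**What to change.** Change the SAP only, before database lock.

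- Keep the two-stratum analyses in 8.3.3 and their interaction tests as planned.
- For each of the six numeric measures, add a prespecified further exploratory model with the score as a continuous term, including its interactions with treatment and visit. Report the modifier-by-treatment contrast at V4, built as in SAP 8.3.2 for the haplotype.
- Report both codings for every measure, and do not choose between them by AIC or by p-value. A spline plot is optional and descriptive.
- Leave smoking and migraine binary. Leave the two ordinal ratings as planned, since a linear term would need an assumed spacing between categories.
- Record the addition in SAP section 11, which now reports no changes.

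No protocol amendment is needed, because this adds to a list that Protocol 11.4.3 leaves open. No new data are needed. The cost is some SAP wording, six more model fits and exploratory tests, and any spline fits. The downside is that the continuous test has less power than the split if the true effect is a step near the cut (47% to 66% v 73% to 74% in the simulation above); the planned test is kept beside it for that case.
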